APPENDIX B: PHARMACOKINETIC EXTENSIVE SAMPLING TIMEPOINTS

Time	Cycle 1 (4 Weeks)							Cycle 2 (4 Weeks)		Every even-numbered cycle thereafter (4 Weeks)		EOT		
	D1				D2	D5	D15		D1 and D15		D1			
	Pre- dose ^a	End of ZW25 infusion	2 h post- dose ^b	4 h post- dose ^b	8 h post- dose ^b	24 h post- dose ^b	96 h post- dose ^b	Pre- dose ^a	End of ZW25 infusion	Pre- dose ^a	End of ZW25 infusion		Pre- dose ^a	End of ZW25 infusion
Allowed time window		+15 min	± 15 min	± 15 min	± 15 min	±4 h	± 4 h	- 4 h	+15 min	- 4 h	+15 min	- 4 h	+15 min	
PK serum sample	X	X	X	X	X	X	X	X	X	X	X	X	X	X ^c

D = day; EOT = End of Treatment; PK = pharmacokinetics

All subjects in Part 1 and at least 6 subjects in Part 2.

^a Relative to the start of ZW25 infusion

^b Relative to the end of ZW25 infusion

^c Only required if the subject has completed less than 6 months of treatment

APPENDIX C: PHARMACOKINETIC SPARSE SAMPLING TIMEPOINTS

Time	Cycle 1 (4 Weeks)				Cycle 2		Every even-numbered cycle thereafter (4 Weeks)		EOT
	D1		D15		D1 and D15		D1		
	Pre-dose ^a	End of ZW25 infusion	Pre-dose ^a	End of ZW25 infusion	Pre-dose ^a	End of ZW25 infusion	Pre-dose ^a	End of ZW25 infusion	
Allowed time window		+15 min	- 4 h	+15 min	- 4 h	+15 min	- 4 h	+15 min	
PK serum sample	X	X	X	X	X	X	X	X	X ^b

D = day; EOT = End of Treatment; PK = pharmacokinetics

Subsequent subjects in Part 2.

a Relative to the start of ZW25 infusion

b Only required if the subject has completed less than 6 months of treatment

APPENDIX D: RESPONSE EVALUATION CRITERIA IN SOLID TUMORS

MEASUREMENT OF EFFECT

Antitumor Effect – Solid Tumors

For the purposes of this study, subjects should be re-evaluated for response every 8 weeks. In addition to a baseline scan, confirmatory scans should also be obtained not less than 4 weeks following initial documentation of objective response.

Response and progression will be evaluated in this study using the new international criteria proposed by the revised Response Evaluation Criteria in Solid Tumors (RECIST) guideline (version 1.1) (Eisenhauer 2009). Changes in the largest diameter (unidimensional measurement) of the tumor lesions and the shortest diameter in the case of malignant lymph nodes are used in the RECIST version 1.1 criteria.

Disease Parameters

Measurable disease: Measurable lesions are defined as those that can be accurately measured in at least one dimension (longest diameter to be recorded) as >20 mm by chest x-ray, as >10 mm with CT scan, or ≥ 10 mm with calipers by clinical exam. All tumor measurements must be recorded in millimeters (or decimal fractions of centimeters).

Malignant lymph nodes: To be considered pathologically enlarged and measurable, a lymph node must be >15 mm in short axis when assessed by CT scan (CT scan slice thickness recommended to be no greater than 5 mm). At baseline and at follow-up, only the short axis will be measured and followed.

Non-measurable disease: All other lesions (or sites of disease), including small lesions (longest diameter <10 mm or pathological lymph nodes with ≥ 10 to <15 mm short axis), are considered non-measurable disease. Bone lesions, leptomeningeal disease, ascites, pleural/pericardial effusions, lymphangitis cutis/pulmonitis, inflammatory breast disease, and abdominal masses (not followed by CT or MRI), are considered as non-measurable.

Note: Cystic lesions that meet the criteria for radiographically defined simple cysts should not be considered as malignant lesions (neither measurable nor non-measurable) since they are, by definition, simple cysts.

“Cystic lesions” thought to represent cystic metastases can be considered as measurable lesions, if they meet the definition of measurability described above. However, if non-cystic lesions are present in the same subject, these are preferred for selection as target lesions.

Target lesions: All measurable lesions up to a maximum of 2 lesions per organ and 5 lesions in total, representative of all involved organs, should be identified as target lesions and recorded and measured at baseline. Target lesions should be selected on the basis of their size (lesions with the longest diameter), be representative of all involved organs, but in addition should be those that lend themselves to reproducible repeated measurements. It may be the case that, on occasion, the largest lesion does not lend itself to reproducible measurement in which

circumstance the next largest lesion which can be measured reproducibly should be selected. Previously irradiated lesions should not be chosen as target lesions unless there has been evidence of progression since radiotherapy treatment was given. A sum of the diameters (longest for non-nodal lesions, short axis for nodal lesions) for all target lesions will be calculated and reported as the baseline sum diameters. If lymph nodes are to be included in the sum, then only the short axis is added into the sum. The baseline sum diameters will be used as reference to further characterize any objective tumor regression in the measurable dimension of the disease.

Non-target lesions: All other lesions (or sites of disease) including any measurable lesions over and above the 5 target lesions should be identified as non-target lesions and should also be recorded at baseline. Measurements of these lesions are not required, but the presence, absence, or in rare cases unequivocal progression of each should be noted throughout follow-up.

Methods for Evaluation of Measurable Disease

All measurements should be taken and recorded in metric notation using a ruler or calipers. All baseline evaluations should be performed as closely as possible to the beginning of treatment and never more than 4 weeks before the beginning of the treatment.

The same method of assessment and the same technique should be used to characterize each identified and reported lesion at baseline and during follow-up. Imaging-based evaluation is preferred to evaluation by clinical examination unless the lesion(s) being followed cannot be imaged but are assessable by clinical exam.

Clinical lesions: Clinical lesions will only be considered measurable when they are superficial (e.g., skin nodules and palpable lymph nodes) and ≥ 10 mm diameter as assessed using calipers (e.g., skin nodules). In the case of skin lesions, documentation by color photography, including a ruler to estimate the size of the lesion, is recommended.

Chest x-ray: Lesions on chest x-ray are acceptable as measurable lesions when they are clearly defined and surrounded by aerated lung. However, CT is preferable.

Conventional CT and MRI: This guideline has defined measurability of lesions on CT scan based on the assumption that CT slice thickness is 5 mm or less. If CT scans have slice thickness greater than 5 mm, the minimum size for a measurable lesion should be twice the slice thickness. Magnetic resonance imaging is also acceptable in certain situations (e.g., for body scans).

Response Criteria

Evaluation of Target Lesions

Complete Response (CR): Disappearance of all target lesions. Any pathological lymph nodes (whether target or non-target) must have reduction in short axis to < 10 mm.

Partial Response (PR): At least a 30% decrease in the sum of the diameters of target lesions, taking as reference the baseline sum diameters

Progressive Disease (PD): At least a 20% increase in the sum of the diameters of target lesions, taking as reference the smallest sum on study (this includes the baseline sum if that is the

smallest on study). In addition to the relative increase of 20%, the sum must also demonstrate an absolute increase of at least 5 mm. (Note: the appearance of one or more new lesions is also considered progressions).

Stable Disease (SD): Neither sufficient shrinkage to qualify for PR nor sufficient increase to qualify for PD, taking as reference the smallest sum diameters while on study

Evaluation of Non-Target Lesions

Complete Response (CR): Disappearance of all non-target lesions and normalization of tumor marker level. All lymph nodes must be non-pathological in size (<10 mm short axis)

Note: If tumor markers are initially above the upper normal limit, they must normalize for a subject to be considered in complete clinical response.

Non-CR/Non-PD: Persistence of one or more non-target lesion(s) and/or maintenance of tumor marker level above the normal limits

Progressive Disease (PD): Appearance of one or more new lesions and/or unequivocal progression of existing non-target lesions. Unequivocal progression should not normally trump target lesion status. It must be representative of overall disease status change, not a single lesion increase.

Although a clear progression of “non-target” lesions only is exceptional, the opinion of the treating physician should prevail in such circumstances, and the progression status should be confirmed at a later time by the review panel (or principal investigator).

Evaluation of Best Overall Response

The best overall response is the best response recorded from the start of the treatment until disease progression/recurrence (taking as reference for progressive disease the smallest measurements recorded since the treatment started). The subject’s best response assignment will depend on the achievement of both measurement and confirmation criteria.

For Subjects with Measurable Disease (i.e., Target Disease)

Target Lesions	Non-Target Lesions	New Lesions	Overall Response	Best Overall Response ^a
CR	CR	No	CR	>4 wks. Confirmation ^b
CR	Non-CR/Non-PD	No	PR	>4 wks. Confirmation ^b
CR	Not evaluated	No	PR	
PR	Non-CR/Non-PD/not evaluated	No	PR	
SD	Non-CR/Non-PD/not evaluated	No	SD	documented at least once >4 wks. from Cycle 1 Day 1 ^b
PD	Any	Yes or No	PD	no prior SD, PR or CR
Any	PD ^c	Yes or No	PD	
Any	Any	Yes	PD	

CR = complete response; PD = progressive disease; PR = partial response; SD = stable disease; wks = weeks.

^a See RECIST version 1.1 manuscript for further details on what is evidence of a new lesion.

^b Only for non-randomized trials with response as primary endpoint.

^c In exceptional circumstances, unequivocal progression in non-target lesions may be accepted as disease progression.

Note: Subjects with a global deterioration of health status requiring discontinuation of treatment without objective evidence of disease progression at that time should be reported as “*symptomatic deterioration*.” Every effort should be made to document the objective progression even after discontinuation of treatment.

For Subjects with Non-Measurable Disease (i.e., Non-Target Disease)

Non-Target Lesions	New Lesions	Overall Response
CR	No	CR
Non-CR/non-PD	No	Non-CR/non-PD ^a
Not all evaluated	No	not evaluated
Unequivocal PD	Yes or No	PD
Any	Yes	PD

CR = complete response; PD = progressive disease; SD = stable disease.

^a Non-CR/non-PD” is preferred over “stable disease” for non-target disease since SD is increasingly used as an endpoint for assessment of efficacy in some trials so to assign this category when no lesions can be measured is not advised.

Duration of Response

Duration of overall response: The duration of overall response is measured from the time measurement criteria are met for CR or PR (whichever is first recorded) until the first date that recurrent or progressive disease is objectively documented (taking as reference for progressive disease the smallest measurements recorded since the treatment started).

The duration of overall CR is measured from the time measurement criteria are first met for CR until the first date that progressive disease is objectively documented.

Duration of stable disease: Stable disease is measured from the start of the treatment until the criteria for progression are met, taking as reference the smallest measurements recorded since the treatment started, including the baseline measurements.

Progression-Free Survival

PFS is defined as the duration of time from start of treatment to time of progression or death, whichever occurs first.

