3.1.4 Part 2 Anti-tumor Activity

The primary objective of Part 2 of the study is to evaluate the potential anti-tumor activity of the recommended dose level of the combination of ZW25 with palbociclib plus fulvestrant in subjects with a diagnosis of HER2-positive, HR-positive breast cancer that is locally advanced (unresectable) and/or metastatic.

Enrollment for Part 2 will begin once the recommended doses of ZW25 and the other drugs of the combination therapy have been confirmed in Part 1. The treatment and blood collection schedules, treatment cycle duration and imaging evaluation intervals are the same as in Part 1.

Part 2 of the study will evaluate the preliminary anti-tumor activity. All subjects will be assessed for safety and anti-tumor response. The mITT set includes all subjects who receive any amount of ZW25 with palbociclib and/or fulvestrant who had at least one identifiable (target and/or non-target) lesion at baseline and at least one post-baseline disease assessment or discontinued all study treatment and are no longer being followed for efficacy. The primary efficacy endpoint will be PFS6 (defined as the % of mITT subjects with PFS of ≥ 24 weeks); secondary efficacy endpoints include ORR, DOR, DCR, PFS, and OS. Approximately 50 subjects are expected to be enrolled in Part 2. Assuming the observed PFS6 rate is between 40% and 70%, the corresponding 95% binomial exact confidence intervals (CI) are summarized in [Table 4](#) below.

Table 4: PFS6 Rate and Corresponding 95% Confidence Intervals

PFS6 Rate	Binomial exact 95% CI (N=50)
40%	(26%, 55%)
50%	(36%, 64%)
60%	(45%, 74%)
70%	(55%, 82%)

Therefore, a total of up to approximately 86 subjects may be enrolled across the entire study.

If possible, an additional optional tumor biopsy may be obtained at the time of disease progression from an accessible site to allow for assessment of changes in HER2 expression as well as the presence of other exploratory biomarkers. Biomarkers of response may be evaluated.

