3.2.3 Blinding and Randomization

This is an open-label, non-randomized study.

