6.4 End of Treatment (EOT) Visit

The EOT visit will be performed for subjects who are withdrawn from treatment for any reason and will take place as soon as possible after a subject permanently stops all study treatment (within 14 days after the last dose of study drug [ZW25, palbociclib, and/or fulvestrant]) unless delayed due to an AE. However, EOT evaluations must be performed before initiation of subsequent therapy. The date the subject met criteria for treatment discontinuation and the reason for treatment discontinuation will be recorded.

- Optional tumor biopsy (and ProSigna assessment on tumor biopsy) at disease progression if the subject provides additional consent
- Disease assessment per RECIST 1.1 (CT/ MRI scans, and breast cancer serum tumor markers [if being monitored], not required if ≤ 4 weeks since previous scan)
- Bone scan (scintigraphy) (not required if ≤ 4 weeks since previous scan): For subjects with new lesions identified by post-baseline bone scintigraphy, targeted assessment by X-ray, CT scan with bone windows, or MRI will be performed to confirm findings.
- Brain scan (MRI) (not required if ≤ 4 weeks since previous scan): After screening, brain scans will be required per protocol only for subjects with findings on the screening brain scan; for subjects without findings on the screening brain scan, subsequent brain scans will be done per institutional standard of care.
- Physical examination, including weight
- ECOG PS
- Vital signs
- Hematology and serum chemistry (plasma chemistry allowed if serum chemistry not available) panels
- Pregnancy test (if applicable)
- Single 12-lead ECG
- Echocardiogram/MUGA (not required if ≤ 3 months since last scan)
- ADA sample
- ctDNA sample (only at time of disease progression, if applicable)
- PK assessment samples (only if the subject has completed < 6 months of treatment)

6.5 Safety Follow-up (Approximately 30 Days After the Last Dose of Study Drug [ZW25, Palbociclib, and/or Fulvestrant])

Approximately 30 days after the last dose of study drug, all subjects will have a follow-up visit, which will include the following assessments.

- Disease assessment per RECIST 1.1 (CT/MRI scans, and breast cancer serum tumor markers [if being monitored], not required if done at EOT visit or ≤ 4 weeks since previous scan)

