9.3.5.4 Disease Control Rate (DCR)

Disease control is defined as a best response of CR, PR, non-CR/non-PD (for subjects who have only non-target lesions), or SD per RECIST 1.1. The proportion of subjects who achieve a disease control response and the corresponding exact binomial 95% CI will be calculated.

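### Footnote b in Appendix D switches off the 4-week minimum for stable disease, and non-CR/non-PD has none, so one early end-of-treatment scan can count towards DCR

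*Combined protocol and SAP*

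**What the plan says.** Section 9.3.5.4 sets the endpoint: "Disease control is defined as a best response of CR, PR, non-CR/non-PD (for subjects who have only non-target lesions), or SD per RECIST 1.1". It gives no minimum time on study.

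The only timing rule is in the best-overall-response table of Appendix D for subjects with measurable disease. The SD row asks that SD be "documented at least once >4 wks. from Cycle 1 Day 1" and carries superscript b. Footnote b reads "Only for non-randomized trials with response as primary endpoint".

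On the two conditions in that footnote:

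- Section 3.2.3: "This is an open-label, non-randomized study".
- Section 3.1.4: "The primary efficacy endpoint will be PFS6", and "secondary efficacy endpoints include ORR, DOR, DCR, PFS, and OS". The Part 1 primary endpoints (Section 2.1) are safety endpoints.

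The companion table, headed "For Subjects with Non-Measurable Disease (i.e., Non-Target Disease", has columns for non-target lesions, new lesions and overall response. It has no best-response or timing column.

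On early scans, Section 6.4 states: "The EOT visit will be performed for subjects who are withdrawn from treatment for any reason". That visit falls within 14 days of the last dose and includes a RECIST assessment, waived only if the previous scan is 4 weeks old or less.

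**The concern.** DCR is meant to show that disease was held for some time. If neither SD nor non-CR/non-PD has an operative minimum, a subject who stops all three drugs in the first weeks, for toxicity or by choice, and has one unchanged scan on leaving treatment is counted as controlled. Later progression does not reverse this. Best response is the best recorded from the start of treatment, and the measurable-disease table assigns PD as best response only when no SD, PR or CR came first.

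The error can only raise DCR. There is also a reproducibility problem: one programmer may apply the 4-week rule and another may follow the footnote, and they would report different DCRs from the same data.

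**Working it through.** **Step 1. Does footnote b apply?** It has two conditions. The study is non-randomized, so the first is met. Response is not a primary endpoint in either part, so the second is not. Read literally, the SD minimum is inoperative.

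**Step 2. Which scans can fall at 28 days or less after Cycle 1 Day 1?**

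- *Scheduled scans.* The first is at Cycle 2 Day 28, which is study day 28 + 28 = 56, or 55 days after Cycle 1 Day 1. With the ±7-day window it falls at 48 to 62 days. Never affected.
- *Safety follow-up scans.* These are about 30 days after the last dose (window +7 days), and the last dose cannot precede Cycle 1 Day 1. They fall at about day 30 or later. Not affected.
- *EOT scans.* Let b be the days from baseline scan to Cycle 1 Day 1 (0 to 28, Section 6.2) and s the days from Cycle 1 Day 1 to the EOT visit. The scan is required when b + s > 28, that is from s = 29 − b.

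| Baseline scan, days before dosing (b) | EOT scan required from (s) | Affected range of s |
|---|---|---|
| 28 | 1 | 1 to 28 |
| 21 | 8 | 8 to 28 |
| 14 | 15 | 15 to 28 |
| 7 | 22 | 22 to 28 |

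Example: b = 14 and s = 20 give 34 > 28, so the scan is required. If it shows SD or non-CR/non-PD, the subject counts as controlled.

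- *Unscheduled scans* in the same 28 days have the same effect.

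**Step 3. Effect per subject.** 1/50 = 2.0 points. If six Part 1 subjects treated at the recommended dose are pooled, as Section 9.3.5 allows, 1/56 = 1.8 points.

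The plan states no DCR figure to reproduce. As a check on the interval method, Clopper-Pearson at 20/50 gives 26.4% to 54.8%, which matches the 40% row of Table 11. Illustration with assumed counts:

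| Controlled | DCR | Exact 95% CI |
|---|---|---|
| 30/50 | 60% | 45.2% to 73.6% |
| 31/50 | 62% | 47.2% to 75.3% |
| 33/50 | 66% | 51.2% to 78.8% |

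**Step 4. Effect in aggregate (assumed inputs).** Suppose a fraction r of subjects stop all drugs with the last dose L uniform over days 7 to 42 and the EOT visit D uniform over 0 to 14 days later.

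- Share of these with an EOT visit by day 28: mean of (28 − D − 7)/35 = (21 − 7)/35 = 0.40.
- Share whose scan is also required under the waiver: 0.29 if the baseline scan is uniform over the 4 weeks before dosing, 0.19 if uniform over the last 2 weeks.
- Share who are non-PD on that scan and have no later non-PD scan: 0.196 and 0.128. This takes exponential PFS with 40% or 50% progression-free at 24 weeks, the next scan 8 weeks later, and new therapy starting at a mean of 8 weeks after stopping.

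| r | Baseline over 4 weeks | Baseline over 2 weeks |
|---|---|---|
| 5% | 0.05 × 0.196 = 1.0 points | 0.05 × 0.128 = 0.6 points |
| 10% | 2.0 points | 1.3 points |
| 15% | 2.9 points | 1.9 points |

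Requiring that no progression precedes the stop moves the extremes only slightly, to 0.7 and 3.2 points. Leaving out the scan waiver would give about 1.4 to 4.1 points, which overstates the effect.

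**The case against.** The best defence is that the SD rule is plainly meant to operate. Appendix D says best response depends on both measurement and confirmation criteria. The Amendment 3 log shows the sponsor moving the anchor of this row from baseline to Cycle 1 Day 1, which would be pointless for a dead rule. Footnote b may be leftover template text. This stands as evidence of intent. It does not change the current wording, and it does nothing for non-CR/non-PD, which has no minimum on either reading.

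A second defence is that Sections 9.3 and 9.3.1.6 leave endpoint details and derivations to the SAP, whose text is not in the reviewed document, and that RECIST 1.1 itself is cited. A minimum may exist there. This also stands: only its absence from the reviewed text can be shown. Section 9.3.5.4, unlike the PFS, DOR and OS sections, does not itself refer the reader to the SAP.

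A reader might infer more than the documents support:

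- *That every off-schedule scan before Week 7 is let in by the footnote.* Scans after day 28, including safety follow-up scans, satisfy the >4-week rule anyway.
- *That DCR should be measured against the first scheduled scan, about Week 7, where the gap would be larger.* No section sets a 7-week minimum, so that gap is not an effect of the footnote.
- *That measurable and non-measurable disease are now held to different standards.* With footnote b read literally, neither has a minimum. The difference arises only if the footnote is ignored.

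**Conclusion.** The point holds in a narrow form. As written, a single unchanged EOT or unscheduled scan 28 days or less after Cycle 1 Day 1 counts as disease control, for SD because footnote b disables the minimum and for non-CR/non-PD because none is stated. The bias runs in the favourable direction only.

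Its size is 2 points of DCR per affected subject at N=50, and about 0.6 to 3 points overall (0.3 to 1.5 subjects) under an assumed 5% to 15% stopping in Weeks 1 to 6 without progression. The stop rate, its timing, the age of the baseline scan and the time to new therapy are all assumptions; the documents give none of them.

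Severity is minor. DCR is a secondary endpoint reported with an exact interval some 27 to 29 points wide at N=50, with no test or threshold. A reader might infer that the primary analysis is weakened; it is not, because PFS6 does not use best overall response.

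**What to change.** 1. In Appendix D, remove superscript b from the SD row only. Its use on the CR and PR rows concerns confirmation of response and is a separate decision.
2. Give non-CR/non-PD the same minimum, more than 4 weeks from Cycle 1 Day 1.
3. State the minimum in Section 9.3.5.4 and in the SAP before database lock, with subjects who do not meet it counted as not controlled and kept in the denominator.

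A DCR with a 7-week minimum (first scheduled scan less its window) may be added as an optional sensitivity analysis, not as a correction.

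The cost is wording only, with no new visits or data. DCR becomes slightly less favourable. Because Section 6.5 waives the safety follow-up scan when one was done at EOT, a subject with an early EOT scan may have no further scan for about 8 weeks, so some who were in fact stable will count as not controlled. Reporting how many subjects are in that position makes this visible.
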